2.1 Sample Size Estimations

As the primary aim of this study is to assess the process and feasibility of implementing the AIRQ™, Asthma Checklist, and education resources (PRECISION program) using a telehealth or in-person platform, inferential statistics will not be conducted as part of the primary endpoint, and a formal sample size estimation is not applicable. Each site will target approximately 50 patients with asthma; however, all sites will be capped at 75 patients per site. This cap may be modified depending on individual site recruitment to ensure the targeted sample size is met. Implementing the AIRQ®, Asthma Checklist, and educational resources (PRECISION program) among approximately 50 patients per site will provide sites with enough experience to provide feedback on the outcomes, barriers, benefits, challenges, ease of implementation, and areas for improvement for future integration as a telehealth platform.

3. ANALYSIS SET

- **All enrolled patients:** All enrolled patients who have completed the initial visit with the AIRQ®
- **Web-survey analysis dataset:** All enrolled patients who complete the initial visit and the web survey
- **Primary care cluster dataset:** All enrolled patients at a primary care site who complete the initial visit and the web survey **CCI**.
- **Exacerbation dataset:** Includes EMR or claims data for enrolled patients who completed the initial visit and have available pre-post exacerbation data.
- **Follow-up analysis set:** All enrolled patients who completed the initial visit with the AIRQ® and have at least one follow-up visit completed in the nine-month implementation period with the follow-up AIRQ®. Patients are not required to have a follow-up visit.
- **HCP analysis set:** All health care providers trained on the study who complete the post-study survey and/or qualitative interview

4. EXPOSURE(S) AND OUTCOMES

4.1 Exposures

4.1.1 Definition of Primary Drug Exposure

Not applicable; no drug administered.

4.1.2 Definition of Comparison Drug Exposure

Not applicable; no drug administered.

4.1.3 Participant-completed Exposures

Patients will complete the following measures.

4.1.3.1 AIRQ®

The AIRQ® includes 10 questions concerning patient medication use, asthma symptoms, medical visits, and tests. All response options are in yes/no format with a two-week recall for symptom-based impairment questions (items 1–7) and 12-month recall for exacerbation-based risk questions (items 8–10). The AIRQ® was developed iteratively, and a targeted review of research articles, current asthma guidelines and screeners, grey literature, and a secondary analysis of qualitative patient data informed the initial development of the AIRQ®. Five clinical experts, representing primary care and specialty care (including an allergist/immunologist, two pulmonologists, a nurse PhD researcher, and a family practitioner), academic and community practices, and five geographic regions of the United States (US), participated in five web-based focus groups to further develop the AIRQ®. The AIRQ® was subsequently presented at six advisory board meetings, in which more than 141 clinical experts, practitioners, asthma educators, and patient advocates reviewed and provided additional suggestions for refinement. All participants will complete the AIRQ® at their initial visit, whether in-person or via telehealth. Scoring information is located in Appendix A.

4.1.3.2 Follow-up AIRQ® (AIRQ® 3-month recall version)

A three-month recall version for the exacerbation items of the AIRQ® reduces the risk questions' (items 8–10) recall period to three rather than 12 months. Patients will complete the follow-up AIRQ® at all follow-up visits during the nine-month implementation period (if applicable).

4.1.3.3 ACE Questionnaire

The ACE Questionnaire is a self-administered electronic questionnaire that includes eight questions using a four-point Likert scale (strongly agree, agree, disagree, strongly disagree) and one open-ended question regarding additional comments about their visit or the AIRQ®. Patients who agree will be sent this questionnaire via an e-mailed survey link following their initial visit. Patients are asked to think about how completing the AIRQ® as part of their in-person or telehealth visit may have affected their experience when answering the questions.

4.1.3.6 Sociodemographic Questionnaire

Sites will collect basic participant demographic information on the Clinical CRF—age, gender, and race. Participants who agree will be asked to complete additional demographic questions. This form collects the participant’s ethnicity, living situation, employment, and education, and will be used to describe the sample and assist with interpreting the results. Patients will be sent this questionnaire via an e-mailed web-link following their initial visit.

4.1.4 Clinician-completed Exposures

4.1.4.1 Clinical Case Report Form

For each participant, the clinical site will complete a Clinical CRF during the initial site telehealth or in-person visit. The Clinical CRF serves to characterize patients based on their asthma history, current medications, time since most recent spirometry, the HCP’s rating of the patient’s asthma severity and control, 12-month history of chart-reported exacerbations (when available), Assess component of the Asthma Checklist, and a treatment plan based on AIRQ® score at the initial visit (step-up/step down/no change).

4.1.4.2 Follow-up Clinical Case Report Form

A Follow-up Clinical CRF will be completed for patients with a follow-up visit (telehealth; in-person) during the follow-up period, which will document the HCP’s rating of the patient’s asthma severity and control, chart-reported exacerbations (when available), Assess component of the Asthma Checklist, and a treatment plan based on follow-up AIRQ® score at follow-up visit (e.g., step-up/step down/no change, referral). If sites submit more than one Follow-up Clinical CRF for a patient, the CRF from the first follow-up visit will be included in the primary analyses; additional follow-up AIRQ® assessments will be used to evaluate frequency of use. Novel sites where patients are participating in several asthma coaching sessions will be instructed to complete the Follow-up Clinical CRF for the patient’s final session.

4.1.5 Clinical Site Touchpoint Questions

Evidera will conduct 30-minute conference calls with each clinical site for up to four timepoints (touchpoints) to discuss the use of PRECISION tools, address site questions, and discuss a set of discussion questions that focus on the facilitators and barriers/challenges of implementing the PRECISION program (educational resources). The same touchpoint implementation questions will be asked to all clinical staff participating in each scheduled meeting: Months 1, 2, 3 (optional), and 6.

4.1.6 Post-study Survey

All HCPs who participated in at least 10 telehealth or in-person visits will be invited to complete the Post-study Survey (paper form). The purpose of this survey is to obtain feedback on the implementation of the AIRQ® within each site’s clinical practice (telehealth platform and in-person visit).

4.1.7 Semi-structured Interview Guide

A semi-structured interview guide will be used by the interviewer to obtain information from the principal investigator and key clinical site staff, including one non-prescriber where available, to gain a deeper understanding of the feasibility of implementing the AIRQ® via telehealth and in-person, as well as sustainability of using the PRECISION program in their clinical practice. Up to three interviews will be conducted per site. The semi-structured interview guide will include an introduction and specific questions/probes designed to facilitate discussion and optimize consistency across interviews. The interview guide will elicit from site personnel the process for implementing the AIRQ®, and recommendations for improving processes related to telehealth and in-person implementation. Also, any specific initiatives that were integrated into various practices will be discussed. Additional unscripted probes may also be used to gain further information or clarification.

[figure not shown]
4.2 Outcomes

4.2.1 Primary Outcome

To address the primary objective of assessing the process and potential benefits when integrating the AIRQ® PRECISION program on a telehealth or in-person platform, the following outcomes will be assessed:

- **Post-study Telehealth Survey:** Descriptive statistics (n, frequency, mean, and standard deviation [SD]) will be used to summarize the results from the Post-study Survey.
- **Qualitative Interviews:** Results from the qualitative interviews will be summarized in a tabular format, with key recommendations, advantages, and disadvantages grouped. Specifically, barriers, benefits, challenges, ease of implementation, and areas for improvement will be summarized. Also, the summary will capture if the PRECISION program has been utilized in clinical practice post-implementation, or what would need to be done to support the continued use of the PRECISION program in their clinical practice.
- **Implementation Touchpoint Discussion with Sites:** Key findings from the implementation questions discussed during the clinical site touchpoint meetings (including barriers and subsequent ways in which these barriers were addressed) will be summarized.

Qualitative findings from the interviews and implementation touchpoints will be interpreted in the context of the Knowledge-to-Action Framework (Graham et al. 2006; Singh et al. 2020), which describes a process to translate new knowledge into sustainable evidence-based interventions that can be applied in clinical practice (In-text Figure 1). In this context, the findings will be used in the action cycle to identify challenges, barriers, and benefits to implementing the AIRQ® and PRECISION tools into clinical practice. The knowledge will be evaluated in local contexts (e.g., practice clusters) and will be monitored throughout the implementation and sustainability period.

In-text Figure 1. Knowledge-to-Action Framework**4.2.2 Secondary Outcome(s)**

1. To address the secondary objective of assessing patient telehealth or in-person visit satisfaction when the AIRQ® is initiated as part of a telehealth or in-person visit with their HCP, the following outcomes will be assessed:
 - o ACE Questionnaire Responses: Descriptive statistics (n, frequency, mean, and SD) will be used to summarize by item for all items. In addition,
2. To explore change in AIRQ® scores from initial visit to follow-up visits:
 - o AIRQ® (initial study visit)
 - o Follow-up AIRQ® (follow-up visits)

Results will be presented by practice cluster and platform used (e.g. telehealth vs in-person).

4.2.3 Exploratory Outcome(s)

Statistical analysis plan
D2287L00028 (EVA-26645)

AstraZeneca
27 Sep 2023

CCI

CCI

A large, bold, red logo consisting of the letters 'CCI' in a sans-serif font. The letters are filled with red and have a thick red outline. They are positioned on a solid black rectangular background.

4.3 Other Variables and Covariates

The sample will be characterized by practice cluster: (1) primary care sites (e.g., private practice, FQHC); (2) specialty care sites (pulmonary, asthma/immunology); and (3) novel sites (e.g., pharmacy, nurse practitioners, nurse educators, prescribers and non-prescribers, telehealth component of Allergy and Asthma Network).

5. ANALYSIS METHODS

5.1 Statistical Methods – General Aspects

An overall data disposition figure (Figure 1) will be generated on all enrolled patients to describe total enrolled/consented, total sample included/excluded from analyses, and finally key data (AIRQ®) availability status. In the data disposition figure, the total sample who had a follow-up visit will be reported by practice cluster. A patient disposition table will also be developed to descriptively characterize the sample in terms of total patients enrolled, age group, and language by site and practice cluster (Table 1a to Table 1c). Descriptive statistics (n, frequency, mean, median, and SD) will be used to characterize the sample in terms of the patient-reported sociodemographic and clinical characteristics (e.g., age, sex, education, etc.) (Table 2a and Table 2b, respectively), overall and by practice cluster. Descriptive statistics (n, frequency, mean, median, and SD) will be used to characterize the sample overall and by cluster type in terms of clinician-reported patient characteristics, clinical characteristics, and visit information (Tables 3a to 3f).

Descriptive statistics (n, mean [SD], median, range) will also be used to present the results (overall and by practice cluster) for the AIRQ® total and control level scores (Table 4a). AIRQ® scores will also be summarized by visit platform (telehealth vs. in-person), exacerbation history, education level, language (sample size permitting), age, sex and NAEPP step level (Table 4b to 4h). Descriptive statistics (n, mean, SD, median range) will be presented for CCI [REDACTED]

[REDACTED] Descriptive statistics (n, mean [SD], median, range) will be presented for CCI [REDACTED]

[REDACTED] [REDACTED] [REDACTED] [REDACTED] Descriptive statistics (n, %) will be presented for the ACE Questionnaire (item scores) by practice cluster, visit platform, AIRQ® control score, exacerbation history, education level, language, age, sex, and NEPP step level (Table 7 series). Item responses and scores on the patient-reported outcome measures (AIRQ®, CCI [REDACTED] and ACE) will be compared across groups (practice cluster, visit platform, exacerbation history, education level, language, age, sex and NAEPP step level). For continuous variables, ANOVA will be used to compare mean scores across groups; pairwise comparisons between means will be performed using Scheffe's test adjusting for multiple comparisons for more than two groups. For categorical data, chi-square analyses will be used to compare frequencies by groups. No adjustments will be made for multiple groups.

For the follow-up analysis dataset, a patient disposition table will be developed to descriptively characterize the follow-up analysis set in terms of age group, language, race, and education by practice cluster (Table 8a). The mean time to first follow-up visit will be described (n, %) in Table 8b. For the primary care and specialty clusters, the first follow-up clinical CRF will be completed at the patient's first follow-up visit. For the novel cluster sites where patients are receiving multiple asthma coaching sessions, the follow-up clinical CRF will be completed at their final coaching session.

Descriptive statistics (n, %) will be used to describe patients with a follow-up visit by AIRQ® control level at initial visit (Tables 8c). Descriptive statistics (n, %) will also be used to describe patients with a follow-up visit by exacerbation history, education level, language, age, sex, and NAEPP step level at the initial visit (Tables 8d to 8i). Descriptive statistics (n, %) will be used to describe patients with a follow-up visit by HCP actions at the initial visit overall and by practice cluster (Table 8j to 8m).

Clinical characteristics and visit information from the first follow-up visit will be presented using descriptive statistics (n, mean [SD], median, range) (Tables 9a to 9e). Descriptive statistics (n, mean [SD], median, range) will also be used to present the results (overall and by practice cluster) for the first follow-up AIRQ® scores and control levels (Table 10a). AIRQ® scores from the first follow-up

visit will also be summarized by visit platform (telehealth vs. in-person), exacerbation history, education level, language, age, sex and NAEPP step level (Table 10b to 10h). In Table 10i, descriptive statistics (mean, SD, median, range) will be used to detail the average number of AIRQs® completed by patients overall and in each practice cluster. In Table 10j, AIRQ® scores from the patient's final follow-up (if more than 1 follow-up AIRQ) will be summarized.

5.1.1 Primary Objective: Assess the Process and Potential Benefits of Implementing the AIRQ™, Asthma Checklist, and Educational Resources (PRECISION Program) into Clinical Practice

This analysis will be conducted on the HCP analysis set of clinicians who completed the post-study survey. Descriptive statistics (n, %) will be used to summarize the proportion of responses for each of the categorical items on the post-study survey (e.g., How would you rate the overall ease of implementing the AIRQ™ into your clinical practice using the telehealth platform?). Descriptive statistics (mean [SD], median, range) will be used to summarize the number of patients treated using the PRECISION program (Table 11). Results will be presented overall and by practice cluster.

Qualitative analyses will be conducted to evaluate the frequency of descriptive free-text responses to open-ended questions on the post study survey (e.g., What features of the PRECISION program do you think could be improved?) (Table 12 series), from the qualitative interviews with key site staff and clinicians (Table 13 series), and from the implementation touchpoint calls with key site staff and clinicians (Table 14 series).

5.1.2 Secondary Objective(s): 1) To Assess Patient Visit Satisfaction When the AIRQ™ Is Initiated as Part of a Telehealth or In-Person visit with Their HCP; 2) To explore change in AIRQ® scores from the initial visit to follow-up visit(s)

To assess patient satisfaction with AIRQ®, descriptive statistics (n, %) will be used to summarize patient responses to the ACE Questionnaire overall and by practice cluster (Table 7a). Scores will also be summarized by visit platform (in-person vs. telehealth), AIRQ® control level, education level, age, exacerbation history, and patient language (Table 7 series).

AIRQ® score and control level at the initial visit and Follow-up AIRQ® score and control level at follow-up visit(s) will be explored overall and by practice cluster, and presented using descriptive statistics (n, frequency, mean, SD) (Table 4a, Table 10a and Table 10j). The change in AIRQ® between initial visit and first follow-up visit will be evaluated using paired t-tests for the overall sample, and by practice cluster (Table 15). If the sample size allows, change in AIRQ® score will also be evaluated based on elapsed time from initial visit to follow-up by groups (e.g., 0–3 months; 4–6 months; 7–9 months). In Table 16, shift analyses will be conducted to evaluate change in AIRQ® control score between the initial and first follow-up visit. The frequency of patients improving, maintaining or worsening in AIRQ® control level from initial to first follow-up visit will be described in Table 17. Similarly, shift analyses for AIRQ® control score between the initial and final follow-up visit will be presented in Table 18, and the frequency of patients improving, maintaining or worsening in AIRQ® control level from initial to final follow-up visit will be described in Table 19. If the sample size for additional AIRQ® completions after the first follow-up allows, an additional exploratory analysis will be to explore the trajectory of change in AIRQ® score in relation to visit number and other clinical variables.

Statistical analysis plan
D2287L00028 (EVA-26645)

AstraZeneca
27 Sep 2023

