APPENDIX R. PATIENT SOCIODEMOGRAPHICS QUESTIONNAIRE (ENGLISH VERSION)

Please complete all questions, if possible.

1. *What is your age?* _____ years

2. *What is your sex?*
 male female non-binary Other: _____

3. *What is your ethnic background?*
 Hispanic or Latino
 Not Hispanic or Latino

4. *What is your racial background? (Please mark all boxes that apply with an “X.”)*
 White
 Black or African American
 Asian
 Native Hawaiian or other Pacific Islander
 American Indian or Alaska Native
 Other (specify): _____

5. *What is your current living/domestic situation? (Please mark only one box with an “X.”)*
 Living alone
 Living with a spouse, partner, family, or friends
 Other (specify): _____

6. *How would you describe your employment status? (Please mark only one box with an “X.”)*
 Employed, full-time
 Employed, part-time
 Homemaker
 Student
 Unemployed
 Retired
 Disabled
 Other (specify): _____

7. *What is the highest level of education you have completed? (Please mark only one box with an "X.")*

- Less than high school
- Secondary/high school
- Associate degree, technical or trade school
- College/university degree
- Postgraduate school
- Other (specify): _____

8. What is your household's total income from all sources over the past 12 months?

- Less than \$15,000
- \$15,000 to \$29,999
- \$30,000 to \$44,999
- \$45,000 to \$59,999
- \$60,00 to \$74,999
- \$75,000 to \$99,999
- \$100,000 or more
- Prefer not to answer

9. *How old were you when you were diagnosed with asthma? _____*

10. *Do you smoke?*

- Yes, current smoker
- Not currently, but previous smoker
- No, never smoked

Observational Study Protocol
Study Code D2287L00028 [EVA-26645-03]
Version 2.0
Date June 16, 2022

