Sociodemographic Questionnaire. If a follow-up visit (telehealth or in-person) is conducted during the follow-up period, the clinical site will administer the AIRQ® three-month recall version (regardless of timing of follow-up visit). Sites/HCPs will complete a Clinical Case Report Form (CRF) after the initial visit and after the first follow-up visit (if conducted) for each participant. For the initial and first follow-up visit for which patients complete an AIRQ®, HCPs will be required to review the Assess component of the Asthma Checklist and provide their responses on the CRF; while sites are encouraged to use the AIRQ® for any additional follow-up visits during the study and to provide documentation of the AIRQ® scores, additional CRFs will not be completed by the HCPs.

Additionally, Evidera will host a 30-minute conference call with each clinical site for up to four timepoints (touchpoints) to discuss the implementation of PRECISION tools (i.e., frequency of visits to and the number of portable document format (PDF) file views from study website), assess whether sites are meeting their targets for using the telehealth platform, address site questions, and discuss any challenges of implementing the PRECISION program. These meetings will take place at Months 1, 2, 3 (optional), and 6 and will be used to identify any sites that may benefit from participating in a re-training session. The optional Month 3 touchpoint will be based on whether the site has any difficulties with the study.

Study Population: Clinic staff will invite patients age ≥ 13 years with an HCP-confirmed asthma diagnosis who present for a clinic visit (telehealth or in-person) to complete the AIRQ® and participant questionnaires. Each site will aim to recruit approximately 50 to 75 patients with a total sample size ranging from approximately 750 to 1,500 patients. The number of patients recruited from each site may be modified (i.e., able to recruit > 75 patients) to ensure that the target study sample size is obtained.

Inclusion Criteria: Patients must meet all of the following criteria to be eligible for enrollment:

1. ≥ 13 years of age at the time of enrollment
2. Prior diagnosis of HCP-confirmed asthma
3. Able to read, understand, and speak English or Spanish sufficiently to self-complete or be administered the AIRQ™ via telephone, desktop computer, or mobile device (e.g., smartphone, iPad)

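### In the AIRQ and ACE comparisons by education level, the lowest education category is confounded with age, because 13-17-year-olds are pooled with adults

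*SAP*

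**What the plan says.** - **Eligibility.** Patients qualify if they are "≥ 13 years of age at the time of enrollment" (SAP section 2; same limit in Protocol 3.3). Adolescents and adults form one sample.
- **Education item.** Protocol Appendix R, item 7, asks "What is the highest level of education you have completed". The lowest option is "Less than high school"; above it are four named levels and a free-text option. None means still at school (student status appears only under employment), and no item asks about a parent's education.
- **Who answers.** The item belongs to the optional web survey: "Participants who agree will be asked to complete additional demographic questions" (SAP 4.1.3.6).
- **Comparisons.** SAP 5.1 says that AIRQ and ACE responses and scores "will be compared across groups (practice cluster, visit platform, exacerbation history, education level, language, age, sex and NAEPP step level"). The methods are: "For continuous variables, ANOVA will be used to compare mean scores across groups", with Scheffe pairwise comparisons, and "For categorical data, chi-square analyses will be used to compare frequencies by groups".
- **Secondary objective.** SAP 5.1.2 repeats education as a grouping for ACE, next to age: "AIRQ® control level, education level, age, exacerbation history, and patient language (Table 7 series").
- **Follow-up.** SAP 5.1 also summarises first follow-up AIRQ by education (Table 10 series) and describes patients with a follow-up visit by education (Table 8 series).
- **Age handling.** SAP 4.3 names practice cluster only. No analysis set in SAP section 3 is limited to adults, and the revisions in SAP Appendix B do not mention it.

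**The concern.** For an adult, the lowest education category records a completed history. For a 14-year-old it records only age. Pooling the two gives a group whose mean AIRQ score or ACE response mixes adolescent asthma with the experience of adults who did not finish high school.

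A separate one-way table by age does not help, because it leaves the composition of the education groups unchanged. If scores differ between adolescents and adults for any reason, the lowest education group will differ from the others even when education has no effect. A reader could take that as a finding about literacy or equity. The primary objective is not touched; at stake are a subgroup presentation of a secondary outcome (ACE) and of the AIRQ scores.

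**Working it through.** The documents give no figure for this comparison, so there is nothing to reproduce. The check asks how mixed the lowest category could be and what that would do to the planned test.

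**Inputs, all assumed.** a = share of survey respondents aged 13-17; q = share of adult respondents below high school; c = share of minors who tick the lowest box (1 unless stated).

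**Step 1. Minors' share of the lowest category** = a·c / [a·c + (1 − a)·q].
- a = 2%, q = 20%: 0.02 / (0.02 + 0.98 × 0.20) = 0.02 / 0.216 = 9%.
- a = 5%, q = 10%: 0.05 / (0.05 + 0.95 × 0.10) = 0.05 / 0.145 = 34%.
- a = 20%, q = 5%: 0.20 / (0.20 + 0.80 × 0.05) = 0.20 / 0.24 = 83%.

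| q | a = 2% | a = 5% | a = 10% | a = 20% |
|---|---|---|---|---|
| 5% | 29% | 51% | 69% | 83% |
| 10% | 17% | 34% | 53% | 71% |
| 20% | 9% | 21% | 36% | 56% |

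With c = 1, minors are the majority when a > q/(1 + q), that is above 4.8%, 9.1% or 16.7% for q = 5%, 10% or 20%. If only 80% or 50% of minors tick that box, the 53% at a = q = 10% falls to 47% or 36%.

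**Step 2. Spurious difference.** Let D be the adolescent-minus-adult difference in mean AIRQ score and let education have no effect. With c = 1, no minors are in the higher levels, so the expected difference between the lowest category and the rest is D × (minors' share). For D = −1 point and a share of 34% it is −0.34 point. The sign of D is arbitrary; the documents give no value.

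**Step 3. Effect on the planned ANOVA.** Simulation with five education groups, SD 2.5 (assumed), D = −1, no education effect, two-sided 5% level and 1,500 runs per scenario. N is the number of respondents with education data, also assumed.

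| a, q | Minors' share | Mean difference, lowest vs rest (N = 750) | Rejection rate, N = 375 | Rejection rate, N = 750 |
|---|---|---|---|---|
| 2%, 10% | 17% | −0.17 | 6% | 7% |
| 5%, 10% | 34% | −0.34 | 10% | 16% |
| 10%, 10% | 53% | −0.52 | 20% | 41% |
| 10%, 5% | 69% | −0.69 | 28% | 54% |

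With D = −0.5 and N = 750, the rates in the same four rows are 5%, 7%, 12% and 15%. With D = 0 they stay near 5% throughout (4.4% to 6.2%).

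**Step 4. After the fix.** Restricting the same simulations with D = −1 to adults gives rejection rates of 4.2% to 5.5% and mean differences between −0.03 and +0.01. The chi-square comparisons of ACE items were not simulated, but they pool the same patients without stratifying by age.

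**The case against.** The strongest reply is that the study is descriptive, education is one of eight one-at-a-time groupings, and none is adjusted for another. Education is not named in the visible primary or secondary objectives, nor among the possible ACE subgroups in Protocol 5.1.2. Scheffe comparisons would show that a difference in a continuous score was confined to the lowest group. SAP Appendix B also lists novel-site tables N4d, N7b-N7i, N8e and N10d among those not run for small numbers; judging by the order of groupings in SAP 5.1, these include the education tables. This limits how much rests on the comparison, and it stands. It does not remove the problem: the SAP specifies these tests, and here the overlap is built into the category rather than being an incidental correlation between two factors.

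A reader might infer more than the documents support:
- **That the education result is largely an age result.** This would need the share of minors among respondents, the share of adults below high school, and an age difference in AIRQ or ACE. None is given. Minors could be under a tenth of the category, and with no age difference the test keeps about its nominal level.
- **That all education contrasts are affected.** Only those involving the lowest category are. A few minors may tick a higher level, but they would not drive the contrasts among those levels.
- **That a parent's education is recorded for some minors.** Nothing readable says who completes the survey for a minor. If it happened, fewer minors would fall in the lowest box.

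The table shells are not in the documents and the exploratory sections are redacted, so a regrouping of education or an adult restriction could sit there.

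**Conclusion.** The point holds in a limited form. As written, the education comparisons of AIRQ and ACE confound the lowest category with age, and no readable text deals with it. Under assumed shares of 2-20% minors and 5-20% of adults below high school, and with every minor in that category, minors make up about 9% to 83% of it. Bias follows only if AIRQ or ACE differs between adolescents and adults. With an assumed one-point AIRQ difference, the spurious gap in the simulated scenarios at N = 750 is about 0.2 to 0.7 point. With no age difference the category is still a mixture, but the test is not distorted. The change is worth making because it is cheap and makes the lowest category interpretable.

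**What to change.** Add to SAP 5.1 and 5.1.2: summaries and tests of AIRQ (initial and first follow-up) and ACE by education level include only patients aged 18 or over at enrolment, using the age on the Clinical CRF (Protocol Appendix I, Part 3, item 4); patients aged 13-17 appear as a separate row with their count and are not part of the test. In the tables that only describe who had a follow-up visit by education, keep minors and show them as their own row, since their recorded level is a true description there.

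Stratifying by age or adding age to the model are workable alternatives. A cut at 18 leaves some 18-year-olds still at school in the lowest category, a much smaller residue.

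The cost is a filter in the programs, a slightly smaller n in the education tables and a re-run of those outputs. No new data are needed. SAP Appendix B is written in the past tense, so the re-run tables should be labelled as a change made after the first analyses.
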